## **1.3 Compliance Statement**

This study will be conducted in full accordance with all applicable Children's Hospital of Philadelphia Research Policies and Procedures and all applicable Federal and state laws and regulations including 45 CFR 46, 21 CFR Parts 50, 56, and 312, and the HIPAA Privacy Rule. Any episode of noncompliance will be documented.

---

The investigators will perform the study in accordance with this protocol, will obtain consent and assent (unless a waiver is granted), and will report unexpected problems in accordance with The Children's Hospital of Philadelphia IRB Policies and Procedures and all federal requirements. Collection, recording, and reporting of data will be accurate and will ensure the privacy, health, and welfare of research subjects during and after the study.

## **2 STUDY OBJECTIVES**

### **2.1 Primary Objective**

Assess microvascular perfusion of the heart, kidneys and/or brain using CEUS in patients with confirmed or probable diagnosis of COVID-19.

### **2.2 Secondary Objectives**

Correlate CEUS measures of microvascular perfusion of the heart, kidneys and/or brain to clinical outcomes.

## **3 INVESTIGATIONAL PLAN**

### **3.1 General Schema of Study Design**

This is a pilot study in which 30 subjects with confirmed or probable COVID-19 will undergo CEUS of heart, kidneys and/or brain.

The dosing plan will be weight-adjusted, based on a dose of 0.03 mL/kg. Each patient will receive up to two contrast injections as per the product label/FDA approved guidelines, with a maximum dose of 2.4 mL per injection. Examinations (heart, kidneys, and/or brain) will be made at the same time, as soon as the first product intravenous injection takes place. The examination will last approximately 15 minutes but no more than one hour.

As exploratory analysis, CEUS findings on these patients will be correlated to clinical outcomes (death, mechanical ventilation, heart attack, stroke, and renal failure).

#### **3.1.1 Study Procedures**

The study team will screen hospitalized patients for COVID-19 probable or confirmed cases. Recruitment will occur via medical chart review and/or physician referral.

Study Phase	Screening (telephone )	CEUS Study Encounter
Informed Consent	X	X
Review Inclusion/Exclusion Criteria	X	X
CEUS safety	X	X
Demographics/Medical History	X	X
Clinical Laboratory Evaluation		X

Lumason IV administration		X
CEUS examination		X
Acute Adverse Event Assessment (<20 minutes after contrast administration)		X

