with empirical formula C38H74 NaO10P, has a molecular weight of 745.

---

Study Design	Cross-sectional observational study.
Subject Population	Inclusion Criteria
key criteria for Inclusion and Exclusion:	
 
1. Patient (male/female) hospitalized at CHOP.
 
2. Patient 17 years of age or younger.
 
3. Diagnosis of COVID-19 or high clinical suspicion for COVID-19 despite negative tests (according to the definition of probable case by the ECDC).
 
4. Patients have evidence of cardiovascular compromise, myocardial injury, acute kidney injury, and/or new-onset neurological symptoms.
 
5. Parental/guardian permission (informed consent)
 

	Exclusion Criteria
	
 
1. Medical history of Lumason hypersensitivity
 

Number of Subjects	Total recruitment: 30 patients with confirmed or probable diagnosis of COVID-19.
Study Duration	CEUS has a total duration of approximately 15 minutes including contrast agent injection and image completion.
Study Visit	Subjects will be imaged at bedside at CHOP for approximately 15 minutes.
Efficacy Evaluations	CEUS scans of diagnostic quality, qualitative/quantitative evaluation of microvascular perfusion of heart, kidneys and/or brain in COVID-19 patients, correlation between CEUS and clinical outcomes of COVID-19.
Pharmacokinetic Evaluations	There are no pharmacokinetic evaluations.
Safety Evaluations	All subjects receiving at least one injection of investigational drug will be included in the safety analysis. The frequencies of AEs by type, severity, and temporal relationship to the CEUS scan will be summarized. SAEs (if any) will be described in detail.
Statistical and Analytic Plan	
This is a pilot study with a projected recruitment of 30 children with COVID-19.
 
See Section 5.3 for further detail.

---

---

**DATA AND SAFETY MONITORING PLAN** The safety monitoring for this study is the primary responsibility of the study team. Regular meetings to discuss the outcomes of the study, and of the safety events, will be conducted by the study team. The occurrence of adverse events, serious adverse events and unanticipated events will be reported by the study team in accordance with federal and institutional guidelines, as outlined in Section 7 of this clinical study.

---

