## 3.2 Study Duration, Enrollment and Number of Sites

### 3.2.1 Duration of Study Participation

Study participation will occur during the inpatient stay. Study duration per participant will include telephone screening lasting approximately 5-10 minutes to confirm eligibility for the study and CEUS safety.

The CEUS exam will last approximately 15 minutes but no more than one hour. Only one CEUS scan will be performed per patient.

Clinical outcomes during hospitalization will be documented via chart review. No outpatient follow-up will be performed.

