## 6 STUDY DRUG

### 6.1 Description

Lumason™ is currently FDA approved for use in the evaluation of heart and liver in the pediatric and adult population. Recommended intravenous dose for Lumason™ is weight-based, 0.03mL/kg as an intravenous injection, up to a maximum of 2.4mL per injection. The dosing plan will be weight adjusted, based on a dose of 0.03 mL/kg. Subjects will be monitored for potential side effects for 60 minutes following the final study drug dose. It is currently used clinically at CHOP radiology department for routine diagnostic ultrasound studies.

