## **7 SAFETY MANAGEMENT**

As is standard clinical practice at CHOP, we will follow all current safety standards for CEUS established by the FDA and ACR to provide adequate protection from potential hazards or injuries to subjects. To assure the safety of the participants, all subjects will be monitored for adverse events during the procedure by direct communication through an intercom system and by visual observance. Data will only be transferred between members of the study team, and no identifiable data will be shared with non-CHOP or CHOP individuals who are not on the study team.

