### **7.1 Clinical Adverse Events**

Clinical adverse events (AEs) will be monitored throughout the study.

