### **7.3 Definition of an Adverse Event**

An adverse event is any untoward medical occurrence in a subject who has received an intervention (drug, biologic, or other intervention). The occurrence does not necessarily have to have a causal relationship with the treatment. An AE can therefore be any unfavorable or unintended sign (including an abnormal laboratory finding, for example), symptom, or disease temporally associated with the use of a medicinal product, whether or not considered related to the medicinal product.

All AEs (including serious AEs) will be noted in the study records and on the case report form with a full description including the nature, date and time of onset, determination of non-serious versus serious, intensity (mild, moderate, severe), duration, causality, and outcome of the event.

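### Do the differing adverse event windows leave the safety summary without a usable counting period?

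*Combined protocol and SAP*

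**What the plan says.** The only planned AE analysis is in the Safety Evaluations row of the Protocol Synopsis, for every subject given at least one injection: "The frequencies of AEs by type, severity, and temporal relationship to the CEUS scan will be summarized". The same row promises a detailed description of any serious adverse event (SAE). Section 5.3 contains no safety analysis.

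Four places mention a period of observation:

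- Section 3.1.1, schedule table: "Acute Adverse Event Assessment (<20 minutes after contrast administration". The row does not say which of up to two injections it counts from.
- Section 6.1: "Subjects will be monitored for potential side effects for 60 minutes following the final study drug dose".
- Section 7: "all subjects will be monitored for adverse events during the procedure", by intercom and by direct sight.
- Section 7.1: "Clinical adverse events (AEs) will be monitored throughout the study". Section 3.2.1 adds: "Study participation will occur during the inpatient stay".

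Section 7.3 defines an AE broadly. It states "The occurrence does not necessarily have to have a causal relationship with the treatment" and includes findings "temporally associated with the use of a medicinal product, whether or not considered related to the medicinal product". It requires every AE to be recorded with date and time of onset, intensity, seriousness, causality and outcome. Section 7.4.1 requires a relationship term for each SAE. Section 5.2 lists death, mechanical ventilation, myocardial infarction, stroke and renal failure as secondary endpoints.

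**The concern.** Set beside one another, these sections seem to offer four different windows for one table, and none says which window feeds it. The window matters because of who is enrolled. Section 3.3.1 requires cardiovascular compromise, myocardial injury, acute kidney injury and/or new neurological symptoms, and Section 8.5 describes the subjects as critically ill. Under the Section 7.3 definition, a stroke several days after the injection can count as an AE and is also a Section 5.2 outcome.

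A whole-stay count would then mostly describe severe COVID-19, while a 20- or 60-minute count would mostly describe reactions to the contrast agent. If the choice were open until the data were in, the reported AE frequency could be steered. The synopsis does not list causality among its tabulation factors, so the table alone might not show which kind of event drove the number.

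**Working it through.** The plan states no figure to reproduce. The check has two parts: how far the windows could move the count if they really were rivals, and whether the text makes them rivals.

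**Size if they were rivals.** The documents give n = 30 (Section 5.3) and the 20- and 60-minute limits. They give neither an outcome rate nor a length of stay, so the following are assumptions: x = 1, 3 or 6 subjects with a Section 5.2 event after imaging, and events spread evenly over d = 3, 7 or 14 days.

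- Gap between the two limits, both counted from the final dose: 60 − 20 = 40 minutes. This is a minimum, since the schedule row says under 20.
- Whole-stay proportion x/30 with exact (Clopper-Pearson) 95% interval: 1/30 = 3.3% (0.1 to 17.2); 3/30 = 10% (2.1 to 26.5); 6/30 = 20% (7.7 to 38.6).
- Expected number of those events inside 60 minutes = x/(24d):

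| x | d = 3 | d = 7 | d = 14 |
|---|---|---|---|
| 1 | 0.014 | 0.006 | 0.003 |
| 3 | 0.042 | 0.018 | 0.009 |
| 6 | 0.083 | 0.036 | 0.018 |

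- A summary cut at 60 minutes would therefore most likely show 0/30 of these events, with exact 95% interval 0 to 11.6%.

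The contrast of 0/30 with 1/30 to 6/30 holds only if the summary may be cut at 60 minutes.

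**Whether the text permits that cut.**

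1. None of the four observation sections mentions the summary. Section 7 describes how subjects are watched during the scan. The schedule row is labelled as an acute assessment. Section 6.1 describes monitoring after dosing. Section 7.1 is overall surveillance. These can be nested: the scan and the early check within the longer monitoring, and all of it within the study.
2. Section 7.1 covers the whole study, Section 3.2.1 places participation in the inpatient stay, and Section 7.3 records every AE with its onset time. The synopsis then tabulates by timing relative to the scan, which has most purpose when the table has not already been cut to a short window. Together these favour one table of all recorded AEs, grouped by timing.
3. Type is also a tabulation factor. The reactions described in Section 8.3.2 are mainly nausea, tinnitus, altered taste, pruritus, hypersensitivity, arrhythmia and blood pressure changes. Stroke, renal failure and ventilation would appear on separate lines. The overlap that remains is narrow: arrhythmia, hypotension, and death, which Section 8.3.2 says has followed some reactions.
4. For that overlap, SAEs are described individually and carry a relationship term. Among at most 30 subjects, each can be read case by case.
5. Counting an event both as an AE and as an outcome distorts neither result. Outcomes are correlated with the imaging measures under Section 5.3, and AEs are only described.

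**The case for a change.** The strongest reply is that nesting is an inference. No sentence states it, and it does not tell the analyst where the time bands fall. Section 8.3.2 places serious reactions commonly within 30 minutes of administration, between the 20- and 60-minute limits, so a band edge at one limit or the other could move an event. The longest window is itself loosely worded. The synopsis row on study duration gives only the scan of about 15 minutes. Section 4.3 mentions only serious, related events after a subject completes, without defining completion. Section 6.1 gives approval for heart and liver, while this study also images kidneys and brain, so readers will treat the AE table as safety evidence.

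The textual points stand. Sections 3.1.1 and 6.1 do not refer to each other, the schedule row does not name its injection, and neither the time bands nor the display of outcome events is written down. The two timings must be reconciled by the sponsor as a matter of wording; which one should govern is not a statistical question.

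The inference to a steerable safety result does not stand. A band edge moves an event from one row of the table to another and does not remove it. Onset times are recorded, so any banding can be rebuilt. Section 3.2.1 speaks directly to participation, and the outcome events are found by chart review in any case. Tabulating by the causality already recorded would be a reasonable courtesy to readers, but it is a reporting preference.

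**Conclusion.** No change to the plan follows. What is missing is a reporting detail: the time bands for one descriptive table and a note on where outcome events are shown. An analyst with onset time, type, seriousness and causality in hand would fill it sensibly, by listing all recorded AEs by type and time since the scan and describing the serious ones.

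The gap of 0/30 against as many as 6/30 is arithmetically right, but it rests on assumed event counts, an assumed length of stay, an even spread of events and a 60-minute cut that no section imposes. It should not be read as the size of a defect. Safety is neither an objective (Section 2) nor an endpoint (Sections 5.1 and 5.2), there is no comparison arm, and no stopping rule depends on the AE count. The choice of bands therefore cannot alter the primary proportion, the perfusion summaries or the outcome correlations.

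This conclusion assumes that AEs are recorded through the inpatient stay with onset times, as Sections 3.2.1, 7.1 and 7.3 together indicate. If recording in practice ended with the scan visit, non-serious later events could go unrecorded and the point would need to be looked at again.

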## 3.2 Study Duration, Enrollment and Number of Sites

### 3.2.1 Duration of Study Participation

Study participation will occur during the inpatient stay. Study duration per participant will include telephone screening lasting approximately 5-10 minutes to confirm eligibility for the study and CEUS safety.

The CEUS exam will last approximately 15 minutes but no more than one hour. Only one CEUS scan will be performed per patient.

Clinical outcomes during hospitalization will be documented via chart review. No outpatient follow-up will be performed.

### 3.2.2 Total Number of Study Sites/Total Number of Subjects Projected

This is a pilot study with a projected recruitment of 30 children with confirmed or probable diagnosis of COVID-19 at the Children's Hospital of Philadelphia.

## 3.3 Study Population

### 3.3.1 Inclusion criteria

1. Patient (male/female) hospitalized at CHOP.
2. Patient 17 years of age or younger.
3. Diagnosis of COVID-19 or high clinical suspicion for COVID-19 despite negative tests (according to the definition of probable case by the ECDC).
4. Patient has evidence of cardiovascular compromise, myocardial injury, acute kidney injury, and/or new-onset neurological symptoms).
5. Parental/guardian permission (informed consent)

### 3.3.2 Exclusion Criteria

1. Medical history of Lumason hypersensitivity.

## 4 STUDY PROCEDURES

Screening will be performed via medical chart review and/or clinical referral of pediatric subjects at the Children's Hospital of Philadelphia. Subjects who fulfill eligibility criteria will be included.

CEUS scan will be performed by CHOP study team members and/or dedicated research ultrasonographers. Subjects will undergo one CEUS exam. The dosing plan will be weight-adjusted, based on a dose of 0.03 mL/kg. Up to two injections per study will be performed as per product label/FDA guidelines. Subjects' and personnel safety will be handled according to clinical protocol for COVID-19.

Organ perfusion will be evaluated in the heart, kidneys and/or brain, provided there is evidence of cardiovascular compromise, myocardial injury, acute kidney injury, and new-onset neurological symptoms. Brain ultrasound will occur if there are new-onset neurological symptoms. We will use a low energy approach to minimize the risk of thermal injury or disruption of the blood-brain-barrier (mechanical index < 0.2 is safe).

Analysis of CEUS imaging by the Principal Investigator will be performed, in addition to medical chart review for clinical outcomes (exploratory analysis).

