**Figure 3.** CEUS of the kidneys. Shown are sagittal CEUS images of the kidneys, (A) demonstrating homogeneous perfusion of normal right kidney with high signal due to intravascular microbubbles and (B) demonstrating low signal regions (yellow arrows) consistent with ischemia.

**CEUS Quantification:** It should be noted that CEUS gives a wide range of quantifiable, continuous parameters reflective of tissue perfusion. Injection of contrast results in increased acoustic signal quantifiable as signal intensity in decibels (dB). Spatiotemporal changes in signal intensity are then measured to reflect tissue perfusion, flow rate, blood volume, and many other parameters that can be derived from the *time intensity curve (TIC)* analysis. In TIC analysis, signal intensity in a given region of interest is plotted over time and parameters are extracted from the curve (for e.g. time to peak or TTP, wash-in area under the curve or WiAUC, rise time or RT, wash-in rate or WiR, wash-in perfusion index or WiPi). This is a well-accepted conventional approach to CEUS quantification previously used by the PI in the report of the first clinical guidelines for application of brain CEUS in infants (29), quantitative detection of hypoxic ischemic injury using brain CEUS (30), and quantification of tumor microvessel density (35). More advanced analysis involves the particle tracking method, in which individual intravascular microbubbles are tracked across thousands of ultrasound frames to quantify microbubble velocity, spatial distribution, trajectory (and other sophisticated parameters such as shear stress, acceleration-deceleration, etc.) (36). The conventional time intensity curve and particle tracking method combined would yield more than >30 continuous CEUS microvascular perfusion parameters that can each, or in combination, be correlated to clinical outcomes in this proposal.

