## 5 STATISTICAL CONSIDERATIONS

### 5.1 Primary Endpoint

1. Estimate the proportion of patients with normal perfusion versus area(s) of hypoperfusion in heart, kidneys and/or brain.

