### 5.3 Sample Size and Statistical Analysis Plan

We will enroll 30 subjects (15 male/15 female) in this pilot study. As part of clinical care, CHOP Radiology also performs approximately 4-5 contrast-enhanced ultrasound cases in a given day, which is higher in volume than any other children's hospital in the country.

---

A sample size of 30 should provide reasonable estimates of the perfusion metrics. For example, a sample size of 30 participants produces a two-sided 95% CI with a width equal to 0.3 when the estimated proportion is as small as 0.3 (95% CI=0.1, 0.5). Also, a two-sided 95% CI with a width equal 0.6 when the estimate of Pearson's product-moment correlation is 0.4 (95% CI= 0.05, 0.7).

Based on microangiopathy/ischemia observed in COVID-19 patients (9-11), we expect our cohort to display delayed perfusion, hypoperfusion or no perfusion of the myocardium, kidneys, and/or brain. Results of the myocardial, renal and brain perfusion will be assessed by two experienced researchers in the field of CEUS and report it qualitatively as either normal or abnormal. In case of diagnosis disagreement between the two raters, a third experienced researcher will confirm the correct diagnosis. Hence, the proportion and frequency of myocardial, renal, and/or brain perfusion abnormalities will be documented. As additional primary analysis, we will also assess quantitative CEUS and derive time-to-peak (TTP) and wash-in area under the curve (WiAUC).

Demographic characteristics and descriptive statistics (such as measures of frequency, central tendency, dispersion, and position) will be summarized for the sample and by male and female sex. The percentage of COVID-19 patients with an abnormal clinical exam will be computed. Time intensity curve analysis will provide further details on the nature of perfusion abnormalities. The following presents the variable names, output, and the reported statistics for the primary and secondary aims.

	Measured Variables	Output and statistics
Primary Analysis	Perfusion defect (hypo- or absent perfusion)	Proportion of COVID-19 patients with perfusion defect
Primary Analysis	Perfusion quantified using time-to-peak (TTP) and wash-in area under the curve (WiAUC) from the time-intensity curve of contrast signal	Summary statistics for TTP and WiAUC, for e.g. mean, standard deviation, 95% CI
Secondary Analysis	Clinical outcomes from chart review etc.	Correlation of CEUS metrics to clinical outcomes

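### Brain CEUS up to age 17 has no acoustic-window rule and no non-diagnostic read, so skull signal loss can be counted as a brain perfusion defect

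*Combined protocol and SAP*

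**What the plan says.** Section 3.3.1 admits any "Patient 17 years of age or younger", with no lower limit. The only exclusion in 3.3.2 is "Medical history of Lumason hypersensitivity". Section 4 ties the brain scan to symptoms alone ("Brain ultrasound will occur if there are new-onset neurological symptoms") and keeps acoustic output low on safety grounds ("mechanical index < 0.2 is safe"). No section mentions a fontanelle, the skull or a bone window.

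The primary endpoint in 5.1 is "Estimate the proportion of patients with normal perfusion versus area(s) of hypoperfusion in heart, kidneys and/or brain". Under 5.3, two experienced readers give each organ a two-way call, and a third settles disagreements. The 5.3 table names the measured event as "Perfusion defect (hypo- or absent perfusion". The same table lists TTP and WiAUC summaries under primary analysis, although 5.2 lists these measures as secondary endpoints. The secondary analysis correlates CEUS metrics with clinical outcomes.

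The synopsis lists diagnostic-quality scans among the efficacy evaluations. It neither defines the term nor links it to an analysis rule.

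**The concern.** Section 1.1 explains that CEUS reads perfusion from acoustic signal intensity, and its kidney example treats low-signal regions as ischemia. Bone in the beam path also lowers signal. In a child whose fontanelle has closed, a weak brain image may therefore reflect reduced perfusion or a poor window, and a two-way scale gives readers nowhere to record which.

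The endpoint is per patient across organs, so one false brain read turns an otherwise normal child into a case. This error is a bias, which the confidence interval does not cover. Brain WiAUC is built from intensity. Pooling fontanelle and transcranial values would mix skull attenuation with perfusion, and age could then confound its correlation with outcome. Section 1.1 says the estimates are meant for designing a future trial, so an inflated proportion would carry forward.

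**Working it through.** **1. The plan's own precision.** Inputs from 5.3: n = 30, p = 0.3, two-sided 95%. The Wald interval is 0.3 ± 1.96 × √(0.3 × 0.7/30) = 0.3 ± 0.164, that is 0.136 to 0.464, width 0.328. This rounds to the stated 0.1 to 0.5 and width 0.3. The precision figure is not in dispute.

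**2. The path from window to endpoint.**
- Who is scanned: any eligible child with new neurological symptoms (3.3.1, 4).
- What is measured: signal intensity over time (1.1).
- What counts as an event: low or absent perfusion (5.3).
- What could stop a poor window being counted: the readers' judgement only. Adjudication applies when two readers disagree, so it does not act on an artefact that both see. Diagnostic quality has no criterion.

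The one premise from outside the documents is general ultrasound physics: bone attenuates the beam.

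**3. Effect per misread.** Each false brain read in a child whose other scanned organs are normal adds 1/30 = 0.033. Starting from 9/30 = 0.30:
- three such reads give 12/30 = 0.40 (Clopper-Pearson 0.227 to 0.594);
- five give 14/30 = 0.467 (0.283 to 0.657), a shift of 0.167, about the whole planned half-width of 0.164.

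**4. Range under assumptions.** The documents give none of these inputs:
- b, the share of children with a brain scan: 0.2 to 0.5;
- s, the share of those scanned through bone: 0.5 to 0.9. The upper value is roughly what ages uniform over 0 to 17 would give with closure at 1 to 2 years: 1 − 1/18 = 0.944 to 1 − 2/18 = 0.889;
- q, the chance that such a scan is read abnormal when the child is truly normal: 0.25 to 1;
- p, the true proportion: 0.30, borrowed from the plan's precision example.

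Shift = (1 − p) × b × s × q. This treats children with brain scans as having the cohort-average chance of a true defect.

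| Case | b | s | q | Shift | Observed |
|---|---|---|---|---|---|
| Low | 0.2 | 0.5 | 0.25 | 0.0175 | 0.32 |
| Middle | 1/3 | 0.9 | 0.5 | 0.105 | 0.405 |
| High | 0.5 | 0.9 | 1 | 0.315 | 0.615 |

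The middle case is about three children (30 × 0.105 = 3.15). Relative to the half-width of 0.164, the shifts are 0.11, 0.64 and 1.92.

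**5. WiAUC and TTP.** If attenuation multiplies the intensity curve by a constant a < 1, WiAUC becomes a × WiAUC, while the time of the peak does not move. WiAUC is thus directly exposed. TTP should be much less so, unless the signal falls close to noise.

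**The case against.** The strongest reply is that the event concerns perfusion, not brightness. Experienced CEUS readers know a poor window when they see one, a third reader is available, and the synopsis names diagnostic quality. This stands in part: some poor windows will be recognised. A reader might infer that every scan through bone yields an image meeting the defect definition. The documents do not support that, and the high case above, with q = 1, is only an outer bound. Yet a reader who recognises a poor window still has no category for it. Dropping the scan informally would leave the denominator undefined and the bias of unknown direction.

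It is also tempting to say that the cited human support for brain CEUS is confined to infants. Section 1.1 refers to infant guidelines, and the titles of references 31 to 33 concern neonates or infants. Reference 30, however, cited for brain CEUS quantification, is titled for pediatric neurosonography generally, and its age range cannot be settled here.

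Section 5.3 can be read as planning organ-level proportions. Heart and kidney figures would then be untouched. The brain figure would take the whole effect on a smaller base: with ten brain scans, an assumed third of 30, each false read is worth 10 points. The per-patient endpoint in 5.1 remains exposed either way.

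Finally, this is a descriptive pilot with no test or decision threshold, and section 4.2 says results do not affect care. That limits the consequence; it does not remove the bias.

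**Conclusion.** The point holds as a gap in the reading and analysis rules. As written, skull attenuation can be scored as a brain perfusion defect and can lower brain WiAUC, and the plan has no step that separates it from true hypoperfusion.

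The size is not known. The firm figure is 3.3 points per false brain read in an otherwise normal child. The range of about 2 to 32 points rests wholly on the assumed share scanned, share through bone, misread rate and true proportion, so no single value in it should be quoted as the expected bias. No bias in TTP is shown. The eligibility range and the output limit are not in question here.

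**What to change.** In 5.1 and 5.3:
- Record the acoustic window for each brain scan: open fontanelle or through bone.
- Let readers classify a brain scan as non-diagnostic, on image-quality criteria written down and applied before the perfusion read. The child still contributes heart and kidneys.
- Give evaluable denominators by organ.
- Report the primary proportion with and without transcranial brain reads.
- Summarise and correlate brain WiAUC separately for fontanelle and transcranial scans. Keep TTP, shown by window.

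Visible contrast in a large vessel such as the circle of Willis should not be required as a gate. Large-vessel signal does not prove that the weaker parenchymal signal is adequate. A child with truly absent cerebral flow would show no such signal and would be removed from the count, biasing the proportion downward.

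The cost is one recorded field, a short quality definition and some table changes, with no added procedure or patients. The downside is that fewer children contribute an evaluable brain result and the brain WiAUC subgroups are smaller.
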